5.1 Imputation rules

5.1.1 Study drug

The following rule should be used for the imputation of the dose end date for a given study treatment component:

Scenario 1: If the dose end date is completely missing and there is no EOT page and no death date, the patient is considered as on-going:

The patient should be treated as on-going and the cut-off date should be used as the dose end date.

Scenario 1 should not be applied for final CSR. All patients should have EOT page complete before the Database lock for Final CSR.

Scenario 2: If the dose end date is completely or partially missing and the EOT page is available:

Please note that date of assessment on EOT eCRF might be very different from last date of dose.

Case 1: The dose end date is completely missing, and the EOT completion date is complete, then this latter date should be used.

Case 2: Only Year(yyyy) of the dose end date is available and yyyy < the year of EOT date:

Use Dec31yyyy

Case 3: Only Year(yyyy) of the dose end date is available and yyyy = the year of EOT date:

Use EOT date

Case 4: Both Year(yyyy) and Month (mm) are available for dose end date, and yyyy = the year of EOT date and mm < the month of EOT date:

Use last day of the Month (mm)

All other cases should be considered as a data issue and the statistician should contact the data manager of the study.

After imputation, compare the imputed date with start date of treatment, if the imputed date is < start date of treatment:

Use the treatment start date

Patients with missing start dates are to be considered missing for all study treatment component related calculations and no imputation will be made. If start date is missing then end-date should not be imputed.

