6.1.5 Treatment duration

The planned duration of study treatment is approximately 36 months (39 cycles).

The Treatment Period for each subject will begin on Cycle 1, Day 1 and continue until the end of Cycle 39 (Week 156), unless treatment change for any reason including treatment failure, e.g. cGvHD progression, mixed response or no response, or a GvHD flare as defined in [Section 6.1.5.2.1](#), intolerable toxicity, death, or withdrawal from the study for other reasons occurs.

During the Treatment period, the subjects' treatment will be managed according to their response as follows:

Subjects that achieve CR or PR: On Cycle 7 Day 1, subjects still receiving benefit from ruxolitinib may continue on ruxolitinib until the end of Cycle 39 (Week 156) and will follow the Visit Evaluation Schedule per [Table 8-1](#):

Subjects that achieve a CR or PR may taper corticosteroids at any time from two weeks of documented CR or PR. See [Section 6.1.5.2](#) for details

In subjects that achieve a CR or PR: A taper of ruxolitinib is allowed only on or after Cycle 7 Day 1.

- A taper of CNI is allowed after Cycle 7 Day 1.

Subjects who taper off ruxolitinib and all immunosuppressive therapy due to achieving a CR or PR will continue to follow the currently assigned Visit Evaluation Schedule ([Table 8-1](#)), including all safety and efficacy assessments, and will be monitored for cGvHD recurrence which must be reported in the database. Subjects experiencing cGvHD recurrence after tapering off ruxolitinib will be treated per Investigator discretion, which may include re-initiation of ruxolitinib and will follow the assigned Visit Evaluation Schedule ([Table 8-1](#)).

Subjects without CR or PR: If the subject is not receiving benefit from ruxolitinib therapy per investigator decision, the subject should discontinue ruxolitinib and be treated per institutional practice.

These subjects will enter the early discontinuation follow-up until completion of 39 cycles from their first dose of ruxolitinib.

Subjects who permanently discontinue ruxolitinib for reasons other than achieving a CR or PR prior to completion of 39 cycles on study will complete the safety follow-up visit and then follow the early discontinuation follow-up visit schedule (as described in [Table 8-1](#)). These subjects may be treated per Institutional practice.

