2.1.1 General definitions

Investigational treatment and study treatment

Investigational treatment, will refer to the ruxolitinib only, while *other study treatment* will refer to concomitant use of corticosteroids to treat treatment-naive cGvHD or SR-cGvHD.

Study treatment, will include both *Investigational treatment* and *other study treatment*.

Date of first administration of study treatment

The date of first administration of study treatment is derived as the first date when a nonzero dose of ruxolitinib was administered as per the DAR eCRF. The date of first administration of study treatment will also be referred as *start of study treatment*.

Date of last administration of study treatment

The date of last administration of study treatment is defined as the last date when a nonzero dose of ruxolitinib was administered as per DAR eCRF. The date of last administration of study treatment will also be referred as *end of study treatment*.

Study day

The study day, describes the day of the event or assessment date, relative to the reference start date.

The study day is defined as:

- The date of the event (visit date, onset date of an event, assessment date etc.) – reference start date + 1 if event is on or after the reference start date;
- The date of the event (visit date, onset date of an event, assessment date etc.) – reference start date if event precedes the reference start date.

The reference start date for all assessments (e.g. safety, efficacy, PK, biomarker, etc.) is the start of study treatment.

The study day will be displayed in the data listings. If an event starts before the reference start date, the study day displayed on the listing will be negative.

Time unit

A year length is defined as 365.25 days. A month length is 30.4375 days (365.25/12). If duration is reported in months, duration in days will be divided by 30.4375. If duration is reported in years, duration in days will be divided by 365.25.

Baseline

For safety and efficacy evaluations, the last available assessment on or before the date of start of study treatment is defined as “baseline” assessment.

If patients have no value as defined above, the baseline result will be missing.

On-treatment assessment/event and observation periods for safety analyses

The overall observation period will be divided into three mutually exclusive segments:

1. ***pre-treatment period***: from day of patient's informed consent to the day before first administration of ruxolitinib.

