2. On-treatment period: from day of first dose of ruxolitinib to 30 days after date of last actual administration of assigned treatment.
3. ***post-treatment period***: starting at Day 31 after last administration of ruxolitinib.

Safety summaries (tables, figures) include only data from the on-treatment period with the exception of baseline data which will also be summarized where appropriate (e.g. change from baseline summaries). In addition, a separate summary for death including on-treatment and post-treatment deaths will be provided. In particular, summary tables for adverse events (AEs) will summarize only on-treatment events, with a start date during the on-treatment period (***treatment-emergent*** AEs).

However, all safety data (including those from the post-treatment period) will be listed and those collected during the pre-treatment and post-treatment period will be flagged. In analyses for the safety disclosure, all AEs collected in the post-treatment period will be included and reported separately.

Subjects who taper off ruxolitinib due to achieving a CR or PR continue efficacy and safety assessments until their EoT visit which may be only after Cycle 39 unless the subject discontinues from study earlier. Safety data from these patients collected after the last study drug intake date + 30 days and before EoT visit will not be included in any safety analyses based on the on-treatment period as defined above. Nevertheless, these data will be listed and flagged in all listings (AEs, lab, vital signs). Subject who tapered off ruxolitinib are identified as they have reason "responder" for ruxolitinib permanent discontinuation on the exposure CRF.

For subjects who tapered off study treatment and later re-started ruxolitinib treatment after a cGvHD recurrence, the on-treatment period is from date of first dose of ruxolitinib to very last dose + 30 days including the period without treatment, which are collected in the database as dose interruption. Safety data (e.g. AEs, labs) collected during this period without treatment will be included in the summary tables as treatment emergent events.

Windows for multiple assessments

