2.4.2.3 Systemic corticosteroid during study treatment

As per protocol the steroid doses of methylprednisolone will be converted to prednisone equivalents by multiplying the methylprednisolone dose by 1.25. Prednisone doses for each subject are converted to mg/kg/day.

The duration of exposure will be summarized for systemic corticosteroid by Age group and disease history of treatment naive-cGvHD or SR-cGvHD at baseline. It will be categorized into time intervals; frequency counts and percentages will be presented for the number (%) of patients in each interval. The actual cumulative dose, dose intensity and relative dose intensity (relative to the starting dose of corticosteroids) will be summarized up to the Cycle 7 Day 1 visit. Graphical display (box plots) will also be generated. These analyses will be based on Safety Set.

For the final CSR these analyses will be done considering data up to end of study/LPLV date.

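### Setting a missing dose end date to the EOT date can place a taper-off responder's last ruxolitinib dose more than two years late, and it records corticosteroid stops at EOT that did not occur

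*SAP*

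**What the plan says.** SAP 5.1.1 sets out the "imputation of the dose end date for a given study treatment component". SAP 2.1.1 defines study treatment as ruxolitinib together with the corticosteroids given for cGvHD, so the rule covers both.

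- Scenario 1, the only route that treats a record as ongoing, needs the EOT page and the death date both to be absent, and it is not to be applied for the final CSR.
- Scenario 2 applies once an EOT page exists. Its Case 1 reads: "The dose end date is completely missing, and the EOT completion date is complete, then this latter date should be used". Case 3 also uses the EOT date when only the year of the dose end is known and it matches the EOT year.
- The same section cautions: "Please note that date of assessment on EOT eCRF might be very different from last date of dose". No exception or cap follows.

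SAP 2.1.1 says that responders who taper off ruxolitinib "continue efficacy and safety assessments until their EoT visit which may be only after Cycle 39 unless the subject discontinues from study earlier". It keeps their safety data from more than 30 days after the last intake up to that visit out of the on-treatment analyses. On corticosteroid exposure, SAP 2.4.2.3 says: "For the final CSR these analyses will be done considering data up to end of study/LPLV date".

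**The concern.** The rule assumes that EOT marks the end of dosing. It does so for a child who stops ruxolitinib early for another reason, because Protocol Table 8-1 schedules EOT within 7 days of the last dose. It fails in two other situations.

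**Ruxolitinib in taper-off responders.** These children stay on the visit schedule without drug, so EOT can fall long after the last dose. Case 1 would count the drug-free interval as exposure. It would also move the end of the on-treatment period, and so reverse the exclusion in SAP 2.1.1. The same period end is a competing-event date in the grade 3 or higher infection analysis (SAP 2.8.4.3).

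**Corticosteroids in early ruxolitinib discontinuers.** EOT is triggered by ruxolitinib (Protocol 8.2.1). A child who comes off ruxolitinib and stays on steroids has an open steroid record because the drug is still being given, not because a date was lost. Case 1 closes that record at EOT. SAP 2.4.1 then computes duration as last date minus first date plus 1, with no censoring.

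At stake are descriptive exposure tables for both drugs and the classification of adverse events as treatment-emergent.

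**Working it through.** **Inputs**

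- Cycle length 28 days and 39 cycles (Protocol 8.2.1); Cycle 7 Day 1 = Day 169 and Cycle 39 Day 1 = Day 1065 (SAP Table 2-1).
- Earliest taper: "A taper of ruxolitinib is allowed only on or after Cycle 7 Day 1" (Protocol 6.1.5). Step length about 56 days (Protocol 6.1.5.2).
- Enrolled: 46, of whom 22, 17 and 7 in Groups 1, 2 and 3 (Protocol, Amendment 2). The analysis sets may be smaller.
- Assumptions: nominal visit days, EOT at the end of Cycle 39, and two taper steps in the illustration.

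**The plan's calendar.** Study day = (cycle − 1) × 28 + 1. Cycle 7 gives 6 × 28 + 1 = 169. Cycle 39 gives 38 × 28 + 1 = 1065. The end of Cycle 39 is 39 × 28 = 1092 days = 156 weeks. All agree with the documents.

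**Ruxolitinib, Case 1.** Error = EOT day − true last-dose day. The illustrative last dose is 169 + 2 × 56 = Day 281.

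| True last dose | Error with EOT at Day 1092 | Years (÷ 365.25) |
|---|---|---|
| Day 169 (theoretical earliest) | 923 days | 2.53 |
| Day 281 (illustrative) | 811 days | 2.22 |
| Day 365 | 727 days | 1.99 |
| Day 726 | 366 days | 1.00 |
| Day 900 | 192 days | 0.53 |

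The error reaches two years only if the last dose is on or before about Day 361 (1092 − 730.5 = 361.5).

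In the illustration, reported exposure is 1092 days against 281, a ratio of 3.9. The true on-treatment period ends on Day 281 + 30 = Day 311. Under Case 1, everything from Day 312 to EOT, 1092 − 311 = 781 days, becomes on-treatment.

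Effect of one such child on mean exposure:

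- Group 1: 811/22 = 37 days
- Group 2: 811/17 = 48 days
- Group 3: 811/7 = 116 days
- All subjects: 811/46 = 17.6 days

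With 0, 3 or 5 affected children, the overall mean moves by 0, 52.9 or 88.2 days (k × 811/46).

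**Ruxolitinib, Case 3.** The true end and EOT share a calendar year, so the error is under one year.

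**Corticosteroids.** Suppose steroids continue to Day 1092 and EOT is 7 days after the last ruxolitinib dose. Days dropped = 1092 − (last ruxolitinib day + 7).

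- Ruxolitinib stopped on Day 169: 1092 − 176 = 916 days (2.5 years).
- Ruxolitinib stopped on Day 726: 1092 − 733 = 359 days.
- EOT at the end of Cycle 39: nothing within the study is dropped.

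These are maxima for a single child. If a steroid instead stopped before EOT and its date is missing, the error runs the other way and duration is overstated.

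**The case against.** The strongest reply is that the rule may rarely act. Protocol 6.5.1.2 requires the ruxolitinib stop date and reason in the eCRF, doses and dose changes go on the dosing record, and missing values are queried before lock (Protocol 11.2). A taper-off responder is identified from a permanent-discontinuation entry, so the child would need that entry without its date. SAP 2.1.1 also defines the last administration from recorded non-zero doses. All of this stands, and the ruxolitinib error may be zero. It does not answer the corticosteroid part, where an open record is an expected state. Nor does the SAP bar imputed dates here, although it does bar completely imputed dates from setting the last contact date.

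It is also fair that continued steroid use may not be observed. The early-discontinuation assessments in Protocol 9.1.1 do not list medications, so true duration may be unrecoverable under any rule. That is a reason to report these records as ongoing, not to enter a stop.

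Three stronger readings are tempting, and the documents do not support them.

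- *Both exposure summaries are biased.* No rate of missing or open dates is given, so bias is possible, not shown.
- *Dose intensity falls to about a quarter (281/1092 = 0.26).* This holds only if cumulative dose is not carried to the imputed date as well. SAP 2.4.1 does not say. If it is carried forward, cumulative dose is inflated and dose intensity falls less.
- *Median steroid duration is wrong by a stated number of months.* That needs the share of early discontinuers and their later steroid use, neither of which is in the documents.

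**Conclusion.** The rule is wrong as written for two identifiable groups. For a taper-off responder with a completely missing stop date, it can place the last dose up to about 2.2 to 2.5 years late, and it contradicts the on-treatment definition in SAP 2.1.1. For an early ruxolitinib discontinuer still on corticosteroids, it enters a stop that did not occur, contradicts the horizon in SAP 2.4.2.3, and can drop up to 916 days when ruxolitinib stops on Day 169.

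The day counts rest on nominal visit days and, for Day 281, on an assumed two-step taper. The overall effect is unknown because it depends on how many end dates are missing or open. The primary ORR does not use dose end dates, and the two secondary steroid endpoints are dose reductions, not durations. The consequences are therefore confined mainly to exposure and safety summaries.

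**What to change.** Amend SAP 5.1.1 as follows.

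1. For subjects whose ruxolitinib discontinuation reason is 'responder', impute a missing end date from the last documented non-zero dosing record, not later than death, and never from EOT.
2. Use the EOT date only for ruxolitinib, and only when the EOT visit is the discontinuation visit.
3. Do not enter EOT as a stop for corticosteroid records still open at that visit. Report them as ongoing, censored at last known use, and give the number of such subjects beside the duration summary.
4. State that an imputed dose end date does not extend the on-treatment period.
5. Report the number of imputed end dates by drug and age group.

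The cost is SAP wording and a small programming change, with no new data. If no ruxolitinib dates are missing, items 1, 2 and 4 leave the ruxolitinib results unchanged. The corticosteroid wording needs correcting in any case.

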5.1.2 AE date imputation

Table 5-5-1 Imputation of start dates (AE, CM) and assessments (LB, EG, VS)

Missing Element	Rule
day, month, and year	
 No imputation will be done for completely missing dates
day, month	
 If available year = year of study treatment start date then 
 If stop date contains a full date and stop date is earlier than study treatment start date then set start date = 01JanYYYY Else set start date = study treatment start date. If available year > year of study treatment start date then 01JanYYYY If available year < year of study treatment start date then 01JulYYYY
day	
 If available month and year = month and year of study treatment start date then 
 If stop date contains a full date and stop date is earlier than study treatment start date then set start date= 01MONYYYY. Else set start date = study treatment start date. If available month and year > month and year of study treatment start date then 01MONYYYY If available month and year < month year of study treatment start date then 15MONYYYY

Table 5-5-2 Imputation of end dates (AE, CM)

Missing Element	Rule (* if end date of the on-treatment period not > (death date, cut-off date, withdrawal of consent date))
day, month, and year	
 Completely missing end dates (incl. ongoing events) will be imputed by the end date of the on-treatment period*
day, month	
 If partial end date contains year only, set end date = earliest of 31DecYYYY or end date of the on-treatment period *
day	
 If partial end date contains month and year, set end date = earliest of last day of the month or end date of the on-treatment period*

Any AEs and ConMeds with partial/missing dates will be displayed as such in the data listings.

Any AEs and ConMeds which are continuing as per data cut-off will be shown as 'ongoing' rather than the end date provided.

The above imputations are only used for analyses of time to and duration of AEs and concomitant medications.

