3. Its relationship to the study treatment (related / not related). If the event is due to lack of efficacy or progression of underlying illness (i.e. progression of the study indication) the assessment of causality will usually be 'Not suspected'. The rationale for this guidance is that the symptoms of a lack of efficacy or progression of underlying illness are not caused by the trial drug, they happen in spite of its administration and/or both lack of efficacy and

progression of underlying disease can only be evaluated meaningfully by an analysis of cohorts, not on a single subject.

4. Action taken with respect to study treatment (dose not changed, dose reduced, drug interrupted, drug withdrawn, not applicable, unknown)
5. Whether Concomitant or additional treatment given due to this adverse event (yes / no)
6. Whether it is serious, where a serious adverse event (SAE) is defined as in [Section 10.1.2](#) and which seriousness criteria have been met.
7. If the event worsens the event should be reported a second time in the eCRF noting the start date when the event worsens in toxicity. For grade 3 and 4 adverse events only, if improvement to a lower grade is determined a new entry for this event should be reported in the eCRF noting the start date when the event improved from having been Grade 3 or Grade 4.

All adverse events should be treated appropriately. If a concomitant medication or non-drug therapy is given, this action should be recorded on the Adverse Event eCRF.

Once an adverse event is detected, it should be followed until its resolution or until it is judged to be permanent, and assessment should be made at each visit (or more frequently, if necessary) of any changes in severity, the suspected relationship to the study treatment, the interventions required to treat it, and the outcome.

All adverse events must be treated appropriately. Treatment may include one or more of the following:

- Dose not changed
- Dose reduced
- Drug interrupted/withdrawn

The following events, which are components of study endpoints: worsening of study indication (cGvHD) including occurrence of cGvHD flare as defined in [Section 6.1.5.2.1](#), relapse or recurrence of underlying hematologic disease (including fatal outcomes), should not be reported as a serious adverse event and will be reported on specific eCRFs other than AE eCRF.

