1.2 Study objectives and endpoints

Objectives and related endpoints are described in [Table 1-1](#) below.

Table 1-1 Objectives and related endpoints

Objective(s)	Endpoint(s)	Analysis	Analysis incl. in final CSR
Primary objective(s)	Endpoint(s) for primary objective(s)	Primary Analysis	

To evaluate the activity of ruxolitinib added to standard dose corticosteroids +/- CNI in pediatric subjects with moderate or severe treatment naive-cGvHD or SR-cGvHD measured by overall response rate (ORR) at Cycle 7 Day 1 based on all subjects in the study.	
Overall response rate (ORR) at Cycle 7 Day 1, defined as the proportion of subjects demonstrating a complete response (CR) or partial response (PR) without the requirement of additional systemic therapies for an earlier progression, mixed response or non-response. The response is assessed per NIH consensus criteria (Lee et al 2015), and scoring of response will be relative to the organ stage at the start of study treatment.	
Refer to Section 2.5.1	No
Secondary objective(s)	Endpoint(s) for secondary objective(s)	Secondary analysis	

To assess pharmacokinetics (PK) of ruxolitinib in treatment-	
Ruxolitinib concentrations by timepoint	
Refer to Section 2.9	No

Objective(s)	Endpoint(s)	Analysis	Analysis incl. in final CSR
naïve cGvHD and SR-cGvHD pediatric subjects			
• To evaluate the safety of ruxolitinib	• Safety and tolerability will be assessed by monitoring the frequency, duration and severity of Adverse Events, including occurrence of any second primary malignancies or infections, and by performing physical exams and evaluating changes in vital signs, tanner stage, chemistry and hematology results from baseline.	• Refer to Section 2.8	Yes
• To assess duration of response (DOR)	• Duration of response (DOR) is assessed for responders only. DOR is defined as the time from first response until cGvHD progression, death, or the date of addition of systemic therapies for cGvHD.	• Refer to Section 2.7.2	Yes
• To estimate ORR at end of Cycle 3	• Proportion of subjects who achieve OR (CR+PR) at Cycle 4 Day 1		No

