2.1 Data analysis general information

The interim and final analysis will be performed by Novartis. SAS version 9.4 or later and/or R version 3.0.2 or later will be used to perform all data analyses and to generate tables, figures and listings.

The analysis cutoff date for the interim analysis of study data will be established when all patients have completed 1 year of treatment or discontinued earlier. The analysis cutoff date for the final analysis of study data will be established when all patients have completed the study.

All statistical analyses will be performed using all data collected in the database up to the data cutoff date. All data with an assessment date or event start date (e.g. vital sign assessment date or start date of an adverse event) prior to or on the cutoff date will be included in the analysis. Any data collected beyond the cutoff date will not be included in the analysis and will not be used for any derivations.

All events with start date before or on the cutoff date and end date after the cutoff date will be reported as 'ongoing'. The same rule will be applied to events starting before or on the cutoff date and not having documented end date. This approach applies, in particular, to adverse event and concomitant medication reports. For these events, the end date will not be imputed and therefore will not appear in the listings.

General analysis conventions

Pooling of centers: Unless specified otherwise, data from all study centers will be pooled for the analysis. Due to expected small number of patients enrolled at centers, no center effect will be assessed.

Qualitative data (e.g., gender, race, etc.) will be summarized by means of contingency tables; a missing category will be included as applicable. Percentages will be calculated using the number of patients in the relevant population or subgroup as the denominator.

Quantitative data (e.g., age, body weight, etc.) will be summarized by appropriate

descriptive statistics (i.e. mean, standard deviation, median, minimum, and maximum).

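### SAP Table 5-5-2 ends ongoing adverse events at last dose + 30 days for duration analyses, so in any AE-duration summary a never-resolved event can score shorter than a resolved one

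*SAP*

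**What the plan says.** SAP Table 1-1 describes the safety endpoint thus: "Safety and tolerability will be assessed by monitoring the frequency, duration and severity of Adverse Events". It marks that endpoint for inclusion in the final CSR.

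For AEs and concomitant medications without an end date, SAP section 5.1.2 (Table 5-5-2) says: "Completely missing end dates (incl. ongoing events) will be imputed by the end date of the on-treatment period". A footnote makes this conditional: "if end date of the on-treatment period not > (death date, cut-off date, withdrawal of consent date". Where only month and year are known, the instruction is to "set end date = earliest of last day of the month or end date of the on-treatment period"; a year-only date is handled in the same way. The section limits the purpose of these rules: "The above imputations are only used for analyses of time to and duration of AEs and concomitant medications". Listings continue to show such events as ongoing.

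SAP section 2.1.1 defines the on-treatment period as running "from day of first dose of ruxolitinib to 30 days after date of last actual administration of assigned treatment".

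Protocol section 10.1.1 sets the follow-up of events: "Once an adverse event is detected, it should be followed until its resolution or until it is judged to be permanent". It also requires a not-resolved outcome to be recorded for an event that is still ongoing.

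**The concern.** An AE that has not resolved has a right-censored duration: all that is known is that it lasted at least until it was last seen. Table 5-5-2 replaces that unknown end with a date tied to dosing, and nothing in the SAP says that the resulting duration is to be treated as censored. An event with a complete end date is not capped, and because the protocol follows events to resolution or permanence, real end dates after last dose + 30 days can occur. The two kinds of event are therefore measured on different scales, and the less favourable outcome gets the shorter scale.

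What would be at stake is the description of persistent toxicity in children. A duration summary built this way would answer how long the event ran within the treatment window, while appearing to answer how long it lasted.

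**Working it through.** The documents state no AE-duration figure, so there is none to reproduce. The check applies the rule as written.

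**Inputs.** End of on-treatment period = last dose + 30 days (SAP 2.1.1). Imputed end of an ongoing AE = that date (SAP Table 5-5-2). Planned follow-up = 39 cycles × 28 days = 1092 days (Protocol 8.2.1). The SAP gives no AE-duration formula; I use end − onset + 1, the convention that SAP 2.4.1 uses for exposure. Onset, stopping and resolution days are illustrative.

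**Reversal of order.** Last dose day 100, so the on-treatment period ends on day 130. Onset day 120.
- Never resolves: 130 − 120 + 1 = 11 days.
- Resolves on day 300, complete date: 300 − 120 + 1 = 181 days.
- Resolves in a month that ends after day 130, day of month missing: the earlier date is day 130, so again 11 days, although the record may place the end in a later month.

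A second case: last dose day 60, onset day 30. Never resolved scores 90 − 30 + 1 = 61 days; resolved on day 200 scores 200 − 30 + 1 = 171 days.

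**Dependence on the stopping day.** Onset day 30, still unresolved at day 1092, so the true duration is at least 1092 − 30 + 1 = 1063 days.

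| Last dose (day) | Scored duration (days) | Shortfall, at least (days) |
|---|---|---|
| 60 | 61 | 1002 (94%) |
| 90 | 91 | 972 (91%) |
| 180 | 181 | 882 (83%) |
| 365 | 366 | 697 (66%) |
| 730 | 731 | 332 (31%) |
| 1092 | to day 1122 | none within planned follow-up |

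**Effect on a summary statistic, under assumptions.** I simulated 100,000 events per setting with exponential durations for resolving events, onset uniform over the days on drug, a fixed share never resolving, and status known to day 1092. The medians below compare the SAP rule, with imputed ends taken as real, against Kaplan-Meier with unresolved events censored.
- Last dose day 60, resolving-event median 60 days: 60 vs 71 days with 10% unresolved, 61 vs 85 with 20%, 60 vs 156 with 40%.
- Last dose day 60, resolving-event median 14 days: 17 vs 17, 20 vs 20 and 33 vs 37.
- Resolving-event median 60 days, 20% unresolved, later last dose: 78 vs 85 at day 365, 79 vs 85 at day 1092.

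The effect on the median ranges from none to large, depending on inputs that the documents do not supply.

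**The case against.** The strongest reply is that no planned AE output uses the rule. SAP 2.8.1 and 2.8.1.2 summarise AEs as numbers and percentages of patients, and the one specified time-to-event analysis of AEs, grade 3 or higher infection in SAP 2.8.4.3, uses start dates. This stands. A reader might infer that the reported safety results are biased; the documents do not support that, because counts, grades and the infection analysis do not depend on AE end dates. What remains is that section 5.1.2 says it serves AE-duration analyses and that duration is in the endpoint.

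Second, the SAP does not say that an imputed end counts as an event. If it were used as a censoring time, unresolved events would not be scored as ended. That also stands, so the conclusion is conditional.

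Third, safety summaries are confined to the on-treatment period, and the cap suits an exposure summary such as that for calcineurin inhibitors in SAP 2.4.2.5.1. That justifies it for concomitant medication. It does not justify capping unresolved AEs while leaving resolved ones uncapped.

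A reader might also see a contradiction with SAP 2.1, which says of ongoing events: "For these events, the end date will not be imputed and therefore will not appear in the listings". Read with section 5.1.2, that sentence works as a listing rule, so a cross-reference is enough.

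**Conclusion.** The point holds as a defect in a stated rule, and it is minor. If an AE-duration summary is produced with the imputed date taken as the actual end, a never-resolved event can score shorter than a resolved one (11 against 181 days in the example), and the shortfall is larger the earlier ruxolitinib stopped. It applies equally to children who taper off as responders, whose on-treatment period also ends at last dose + 30 days although assessments continue. It is smaller for those who restart, whose period runs to the very last dose + 30 days. Where death, cut-off or consent withdrawal falls before last dose + 30 days, the footnote governs and the rule does not apply as shown.

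The size cannot be derived from the documents; the figures above rest on assumed onset, stopping and resolution patterns. Two stronger readings should be resisted. One is a general percentage of understatement obtained by truncating every event still open at last dose + 30 days: that is a different rule, because complete later end dates are kept. The other is that early stopping is mostly due to toxicity: the documents give no data on this, and Protocol 9.1.1 also lists lack of efficacy, relapse, graft failure and pregnancy.

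**What to change.** In SAP Table 5-5-2, separate AEs from concomitant medications.

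- For AEs, do not use the imputed date as an event end. Treat an ongoing AE as right-censored at the last date it was known to be ongoing, and not after death, cut-off or consent withdrawal.
- Do not cut a partial AE end date to before its recorded month or year.
- Summarise any AE duration by Kaplan-Meier and report the number of events not resolved.
- Keep the on-treatment cap for concomitant-medication exposure.
- Cross-reference SAP 2.1 and 5.1.2, so that the listing rule and the analysis rule are clearly distinct.

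The last contact date in SAP Table 2-2 should not be the censoring date. It can come from survival, laboratory or other records, and the early-discontinuation assessments in Protocol 9.1.1 include no general AE review, so it could credit time in which the event was not observed.

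If no AE-duration analysis is intended, the alternative is to say so and delete the rule for AEs. Either way the cost is SAP wording and, if duration is reported, a small program change. Unresolved status is already recorded, so no new data are needed. The downside is that reported AE durations become longer.
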